### 9.3 POPULATIONS FOR ANALYSES

We will conduct intention-to-treat (ITT) analyses where we include all patients based on their randomized groups, regardless of their subsequent withdrawal from treatment or deviation from the protocol. Primary analyses will be based on participants who are evaluated at 6-month follow-up. In the case of missing data, we will collect reasons for dropout to inform our assumption about missing mechanism. Secondary analyses using multiple imputation or inverse probability weighting to account for missing data will be explored. Sensitivity analyses will be performed to explore the effects of departures from assumptions made in these missing-data analyses.

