The Intervention group will receive one to two text message per day for 4 weeks, focusing on building motivation, self-efficacy, and outcome expectations to contact and utilize one or more EBT resources for smoking cessation. Participants will be able to text key words for more information on any one of the EBTs. Participants will receive their first text message within 24 hours of their dental appointment. Message features include polls (text message questions that allow tailoring of subsequent messages), quizzes (interesting questions will be texted to them with answers given the next day), tailoring (e.g., readiness to make contact with an EBT) and interactivity (e.g., participants who requested more information about an EBT will be asked 48 hours later if they contacted the EBT and if not, the program will query the barriers and provide problem solving). There will be two text message curriculums: messages to motivate EBT utilization for those who are not ready to quit and messages to motivate EBT utilization for those who are ready to quit. For participants who are not ready to quit, the curriculum builds on our extensive work with unmotivated smokers. Text messages will focus on addressing myths that surround NRT and other stop smoking medications (e.g., concerns about addiction), take small steps towards making the decision towards EBT utilization, re-emphasis of some of the motivational strategies and concepts used in the video, tips on not getting stuck in ambivalence, and enhancement of outcome expectations. For motivated smokers, we will provide information about the EBT and what to expect, advantages of the EBT (more chances of quitting, less cravings), preparing for cessation, and specific help to connect and facilitate access to EBT. Both text message curriculums will include information on how to contact the EBTs and procure NRT and other smoking cessation medications. After the 4-week text message program has ended, we will send occasional “reminder” text messages throughout the remaining study period (e.g., ending prior to the six-month follow-up questionnaire). These reminder text messages serve two purposes: to remind participants of the EBTs resources for smoking cessation, and as a retention strategy that “fills the gap” in communication during the remaining study period.

Based on the NIH Behavioral and Social Intervention Clinical Trial Protocol Template v3.0 - 20180827

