#### 9.4.2 ANALYSIS OF THE PRIMARY ENDPOINT(S)

Aim 1 Hypothesis 1.1. Between group differences in any EBT utilization. The outcome is any EBT utilization over the 7-month study period, including use of the Quitline, clinic-based programs, NCI’s text message program, nicotine replacement therapy, other evidence-based medication (e.g., Bupropion, Varenicline). Quitline use will be based on objective usage data provided by National Jewish Health (the operator of the state's quitline contracted by the Massachusetts Tobacco Cessation and Prevention Program) (e.g., whether contact was made, number of counseling calls, whether patients set a quit date, whether nicotine replacement was requested and delivered to patients), and engagement with NCI’s text message program use (e.g., whether patients opted into the program, response rates, length of time in the program) will be obtained objectively from the program. Data on other EBT utilization (clinic-based counseling; receipt of smoking cessation meds outside of the quitline) will be based on self-report. This binary outcome will be analyzed through a logistic regression model, with the intervention effect described through an odds ratio and 95% confidence interval. We will control for age, gender, race/ethnicity, and variables identified through preliminary analyses as significantly differing between study groups.

Aim 1 Hypothesis 1.2. Dose of EBT utilization. The outcome is our UIS (described in 9.4.1) which summarizes participation in one or more EBTs (the quitline, nicotine replacement or other medications, the NCI SmokefreeTXT program, and clinic based programs). Multiple linear regression will be used to compare the Intervention vs. Control, controlling for age, gender, race/ethnicity, and variables identified through preliminary analyses as significantly differing between study groups. The intervention effect will be described through the slope, representing the difference in mean UIS for those in the Intervention vs. Control group.

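### The primary analysis is labelled ITT but limited to 6-month completers, so it drops 'yes' outcomes already on record and leaves the odds ratio open to arm-dependent attrition bias

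*Combined protocol and SAP*

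**What the plan says.** Section 9.3 opens with the ITT commitment that "we include all patients based on their randomized groups, regardless of their subsequent withdrawal from treatment or deviation from the protocol". The next sentence sets a narrower set: "Primary analyses will be based on participants who are evaluated at 6-month follow-up". Section 9.4.2 repeats both sentences for the primary endpoints. Missing data are addressed as follows: "Secondary analyses using multiple imputation or inverse probability weighting to account for missing data will be explored". Reasons for dropout are to be collected and sensitivity analyses run around the missing-data assumptions, but no model is given.

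On the binary endpoint, section 9.4.2 says "The outcome is any EBT utilization over the 7-month study period". On its sources it says "Quitline use will be based on objective usage data provided by National Jewish Health", and that SmokefreeTXT engagement "will be obtained objectively from the program". Clinic counselling and medication obtained outside the quitline are self-reported, and section 8.1 schedules EBT assessment at Times 4, 5 and 6. Section 7.3 keeps contacting people who missed earlier surveys, so responses can be intermittent.

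Section 6.1.1 describes texts sent after week 4: "These reminder text messages serve two purposes: to remind participants of the EBTs resources for smoking cessation, and as a retention strategy". Section 4.3 says these go to the Intervention group.

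Section 9.2 removes 20% (lost, or ineligible after randomisation), leaving 364 of 455 and power 0.87. Section 7.1 treats people who cannot or will not wear the headset as ineligible although randomised, section 2.3.3 ends participation for those who take it off, and section 7.2 allows some randomised people to be replaced.

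**The concern.** The stated analysis set contradicts the ITT label, and it fits this endpoint poorly. A cumulative yes/no outcome can be settled as 'yes' long before Day 210, and two of its four sources are program records that need no survey. Someone with a quitline record in month 2 and no 6-month survey is a known user, yet leaves the primary analysis.

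Conditioning on a post-randomisation event also means that the odds ratio compares people who stayed, not the groups as randomised. The reminder texts give a specific reason for care: one exposure, in one arm only, is meant both to prompt EBT use and to hold people in follow-up. That could tie retention to the outcome in the Intervention arm and not in the Control arm. The headline result depends on which analysis is primary, and the alternatives have no committed method.

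**Working it through.** **Inputs from the plan.** Control 22.7%, Intervention 37.6% (OR 2.05), two-sided alpha 0.05, arms of 227 and 228, 20% removed (all section 9.2).

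**1. The plan's power figure.** 455 × 0.80 = 364, or 182 per arm. Two-proportion test with pooled variance under the null:

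- SE0 = √(2 × 0.3015 × 0.6985 / 182) = 0.0481
- SE1 = √((0.227 × 0.773 + 0.376 × 0.624) / 182) = 0.0475
- power = Φ((0.149 − 1.96 × 0.0481) / 0.0475) = Φ(1.15) = 0.875

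This reproduces the stated 0.87. The power statement therefore rests on the restricted set, which supports reading the restriction as survey completion. The same formula with all 455 gives 0.936. That is an upper limit, because imputed outcomes do not restore full information.

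**2. Users among those removed.** If loss is unrelated to outcome: 227 × 0.2 × 0.376 + 228 × 0.2 × 0.227 = 17.1 + 10.4 = 27.4 of 91. The documents do not say what share would already be documented. At 25%, 50% or 75% (assumptions), about 7, 14 or 21 known 'yes' outcomes are discarded.

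**3. When the completer odds ratio is biased.** Let r be the probability of being evaluated, by arm and by EBT use. Then

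observed OR = true OR × (r[Int, user] / r[Int, non-user]) ÷ (r[Ctl, user] / r[Ctl, non-user]).

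If retention depends on use equally in both arms, the factors cancel. If the arms differ only in overall retention, each ratio is 1 and there is no bias. Bias needs the user/non-user retention ratio to differ by arm.

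**4. Size with no true effect.** All retention values are assumptions, since the plan gives none by outcome. Controls are retained at 80% whatever their use. The rejection rate is from the two-sided Wald test on the log OR, using expected cell counts. It is shown for 30% use in both arms (an assumption close to the mean of the two design rates) and for the plan's 22.7%.

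| Intervention users / non-users retained | Observed OR | Rejection, 30% use | Rejection, 22.7% use |
|---|---|---|---|
| 90% / 85% | 1.06 | 0.058 | 0.056 |
| 90% / 80% | 1.13 | 0.082 | 0.077 |
| 95% / 80% | 1.19 | 0.121 | 0.109 |
| 95% / 75% | 1.27 | 0.185 | 0.163 |

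Last row at 30%: cells 64.7, 119.2, 54.7 and 127.7; log 1.267 = 0.236; SE 0.2235; Φ(1.058 − 1.96) + Φ(−1.058 − 1.96) = 0.185. Overall retention is 81% v 80%, so similar attrition totals would not reveal the problem.

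**5. The other direction.** With the design effect true and 65% of Intervention users but 85% of non-users retained: 2.05 × 0.65/0.85 = 1.57; log 1.569 = 0.4505; SE 0.2399; power = Φ(1.878 − 1.96) = 0.47.

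**6. Why not count every missing outcome as non-use.** In the extreme case where all lost participants are counted as non-users, 20% loss per arm gives 30.1% v 18.2%, OR 1.94 and power 0.85 on 455. Loss of 25% v 15% (assumed) gives OR 1.64 and power 0.61. That rule would exchange one arm-dependent distortion for another.

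**The case against.** The plan is not silent on missing data. Imputation or weighting, reasons for dropout and sensitivity analyses are all foreseen, and section 9.4.1 leaves a formal SAP to be completed before unblinding. The sentence on the 6-month evaluation also does not define 'evaluated'. The schedule in section 1.3 lists objective confirmation of EBT use at Time 6, so a milder reading exists in which a program record counts. This lowers the severity but does not remove the point: the planned methods are secondary and unspecified, and the subtraction in section 9.2 weighs against the milder reading.

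Four stronger inferences are tempting and are not supported.

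- **That most of the missing outcome is known.** Without the last survey only a 'yes' is settled. A 'no' to Day 210, and the full utilization index score, still depend on self-report.
- **That all 91 are lost through the 6-month rule.** The 20% also covers people found ineligible after randomisation.
- **That program records are certain to exist for everyone.** Section 2.3.3 describes sharing identifiers with the quitline operator; no matching procedure for SmokefreeTXT is described.
- **That an 18% false-positive rate is to be expected.** It requires Intervention non-users to be retained worse than Controls (75% v 80%), which a retention text does not explain. With non-users at 80% to 85%, the rate is about 6% to 12%.

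The main retention efforts (survey reminders, calls, letters, payments, at least five contact attempts) are described without distinction by arm in sections 5.5 and 7.3, which makes a large arm difference less likely.

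**Conclusion.** The contradiction stands: the primary analysis is called ITT on all randomised patients but is planned on those evaluated at 6 months. On the binary endpoint it discards known 'yes' outcomes, an unknown share of about 27 expected users among the 91 removed (at design rates, with loss unrelated to outcome).

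Bias is a risk and not a certainty, and its direction is unknown. It arises only if retention relates to EBT use differently by arm. The Intervention-only reminder texts make that plausible; nothing in the documents shows that it will happen. With no true effect, the assumed patterns give an odds ratio of about 1.06 to 1.27 and a false-positive rate of about 6% to 18%, the top figure being an upper-end assumption. A reversed pattern would cut the design odds ratio to about 1.57 and power to about 0.47. This should be settled before the SAP is final, because it decides which analysis carries the conclusion.

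**What to change.** In sections 9.3 and 9.4.2 and in the SAP:

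- Make all randomised participants, by assigned arm, the primary analysis set.
- Count any EBT utilization as 'yes' if any source documents use from randomisation to Day 210: quitline record, SmokefreeTXT record, or a report at Time 4, 5 or 6. Use program records for everyone who can be matched, and describe the SmokefreeTXT matching.
- Where no use is documented, prespecify one multiple-imputation model, run by arm, for the self-reported components. Do the same for the missing components of the utilization index score.
- Move the 6-month completer analysis to sensitivity.
- State that people deemed ineligible after randomisation, or replaced, stay in the primary set. Sections 2.3.3, 7.1 and 7.2 must be reconciled with the ITT statement, including what is still collected on these people.

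The cost is wording, an imputation model and somewhat more analysis work, with no extra participants. The drawback is that the primary result then leans partly on the imputation model, so its assumptions need the sensitivity analyses that the plan already foresees. No change to the text-message schedule is needed.

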### 9.4 STATISTICAL ANALYSES

#### 9.4.1 GENERAL APPROACH

For descriptive statistics, categorical data will be presented through percentages and continuous variables will be presented through means and standard deviations. For statistical tests, a two-tailed  $p$ -value less than 0.05 or a 95% confidence interval not including the null value will be used for statistical significance.

EBT utilization will be analyzed by computing a utilization index score (UIS). The UIS will be created by first computing a proportion of utilization score for each of the EBTs for each participant. For example, a participant who completed 4 of 5 quitline calls has a proportion score of 80. For NRT, the recommended length of treatment is 8 weeks and the proportion completed by each participant will be computed. For the NCI smoke-free text message program, the recommended length of participation is 56 days, and we will compute the proportion of days completed, as well as the proportion of text messages responded to (of those that required a response). For clinic-based programs, the proportion will be calculated as the number of sessions attended divided by maximum number of sessions offered at the corresponding clinic. Because participants may use one or more EBT programs, the overall “utilization index score” will be the sum of the above individual proportion scores of each EBT for each person. These individual scores will be summed to obtain the UIS (continuous variable). The distribution of our UIS will be examined for approximate normality, and transformations to improve normality or categorization of the index score will be considered if appropriate. For primary analyses, we will control for age, gender, and race/ethnicity, along with variables identified through preliminary analyses as significantly differing between study groups.

This study will be registered with Clinical Trials.gov prior to the start of participant enrollment.

A formal Statistical Analysis Plan (SAP) will be completed prior to the completion of the study and the unblinding of the study data.

---

#### 9.4.2 ANALYSIS OF THE PRIMARY ENDPOINT(S)

Aim 1 Hypothesis 1.1. Between group differences in any EBT utilization. The outcome is any EBT utilization over the 7-month study period, including use of the Quitline, clinic-based programs, NCI’s text message program, nicotine replacement therapy, other evidence-based medication (e.g., Bupropion, Varenicline). Quitline use will be based on objective usage data provided by National Jewish Health (the operator of the state's quitline contracted by the Massachusetts Tobacco Cessation and Prevention Program) (e.g., whether contact was made, number of counseling calls, whether patients set a quit date, whether nicotine replacement was requested and delivered to patients), and engagement with NCI’s text message program use (e.g., whether patients opted into the program, response rates, length of time in the program) will be obtained objectively from the program. Data on other EBT utilization (clinic-based counseling; receipt of smoking cessation meds outside of the quitline) will be based on self-report. This binary outcome will be analyzed through a logistic regression model, with the intervention effect described through an odds ratio and 95% confidence interval. We will control for age, gender, race/ethnicity, and variables identified through preliminary analyses as significantly differing between study groups.

Aim 1 Hypothesis 1.2. Dose of EBT utilization. The outcome is our UIS (described in 9.4.1) which summarizes participation in one or more EBTs (the quitline, nicotine replacement or other medications, the NCI SmokefreeTXT program, and clinic based programs). Multiple linear regression will be used to compare the Intervention vs. Control, controlling for age, gender, race/ethnicity, and variables identified through preliminary analyses as significantly differing between study groups. The intervention effect will be described through the slope, representing the difference in mean UIS for those in the Intervention vs. Control group.

We will conduct intention-to-treat (ITT) analyses where we include all patients based on their randomized groups, regardless of their subsequent withdrawal from treatment or deviation from the protocol. Primary analyses will be based on participants who are evaluated at 6-month follow-up. In the case of missing data, we will collect reasons for dropout to inform our assumption about missing mechanism. Secondary analyses using multiple imputation or inverse probability weighting to account for missing data will be explored. Sensitivity analyses will be performed to explore the effects of departures from assumptions made in these missing-data analyses.

---

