Rationale for Study Design and Innovation. Previous studies of smoking cessation in dental settings have relied on provider-based counseling, which can be costly in terms of provider training time, time spent delivering the intervention, and monitoring ongoing treatment fidelity. Prior studies suffer from dissipation of treatment effects over time; lack of objective verification of major outcome variables; recruiting only smokers who are ready to quit; and lack of "Arranging follow-up" as recommended by the NCI 5 As. Furthermore, few studies have specifically targeted settings that serve urban and low income smokers. The proposed study will fill in the gaps by: 1) testing the intervention in a fully powered, longitudinal trial, 2) using objective measurement for primary outcomes and for smoking cessation, 3) delivering an intervention that has minimal provider and patient burden, increasing the likelihood that it will be disseminated, 4) using a novel method of delivering an intervention while clinical care is being provided and without a loss of treatment fidelity, 5) targeting all smokers—not only those who are ready to quit, and 6) testing mechanisms of change. This study attempts to bridge the gap between dentistry and cessation services.

Study Design: The aim of the study is to test whether a video-based smoking cessation induction intervention delivered through a VR headset during dental cleanings increases utilization of EBTs for smoking cessation. Specifically, we will assess utilization of the following EBTs: the Massachusetts State quitline (operated by National Jewish Health), clinic-based programs (e.g., community health centers, hospital smoking cessation clinics), National Cancer institute's (NCI) text message program (SmokefreeTXT), nicotine replacement therapy (NRT) products, and non-NRT smoking cessation medications. 437 smokers will be randomized to either the Intervention consisting of: 1) smoking

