## 9.2 SAMPLE SIZE DETERMINATION

Power calculations focus on the comparison of those randomized to the Intervention vs. Control on our primary outcome of any EBT engagement through a chi-square test at the two-sided  $\alpha = 0.05$  level. We will not adjust p-values for multiple comparisons.

Using the odds ratio as our effect size, we estimate the effect of the Intervention will be  $OR=2.05$  (corresponding to percent with any EBT utilization of 22.7% in the Control vs. 37.6% in the Intervention). Only two published studies tested the efficacy of an intervention on EBT utilization rate, both at 12-months follow-up. Brooks et al reported an EBT utilization rate (i.e., Quitline or clinic-based program) of 29.8% in the intervention group vs. 14.7% in controls ( $OR=2.4$ ). Fu et al reported an EBT utilization rate (counseling or medications) of 44.2% in the intervention and 30.6% in controls ( $OR=1.8$ ). Therefore, we use the average EBT utilization rate in the control groups from these studies (22.7%) as our ‘any EBT utilization’ rate under the null hypothesis in the power analysis. Because neither of the above studies used video or were conducted in a dental setting, we also considered previous studies testing the effectiveness of videos on cessation, which report ORs of 1.9 and 3.0, and previous studies on cessation in dental settings (meta-analysis  $OR=2.38$ ). Based on all the above, we conservatively chose an anticipated effect size of  $OR=2.05$  (corresponding to rates of 22.7% vs. 37.6%). With  $\alpha=0.05$  (two-sided), we need a total sample of  $n=300$  subjects to achieve 0.80 power of detecting this anticipated effect. However, because of potential differences between clinic sites, and assuming an attrition rate of 20% (lost to follow-up or ineligible post-randomization), in consultation with the NIDCR in April 2024 we received authorization to increase the sample size to  $n=455$  subjects ( $n=227$  for intervention and  $n=228$  for control group). Therefore, with  $\alpha=0.05$ , the anticipated effect size of  $OR=2.05$ , and 364 subjects (455 minus 20% lost to follow-up or ineligible post-randomization), we will have 0.87 power to detect the anticipated effect.

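### The primary endpoint of any EBT utilization merges program records with self-report, and no planned analysis separates the two

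*Combined protocol and SAP*

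**What the plan says.** Under Hypothesis 1.1 in Section 9.4.2, any EBT utilization over 7 months is a single yes/no outcome, analysed by one logistic regression. Quitline use comes from the vendor's records and SmokefreeTXT use from that program. For the remaining sources: "Data on other EBT utilization (clinic-based counseling; receipt of smoking cessation meds outside of the quitline) will be based on self-report". Section 8.1 gives the same split and notes that medication data may be of either kind, depending on how the medication was obtained. One positive answer on a self-reported item is enough to make a participant a user.

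Section 2.1 lists "using objective measurement for primary outcomes and for smoking cessation" among the ways the trial improves on earlier work.

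On the analysis set, Section 9.4.2 states: "Primary analyses will be based on participants who are evaluated at 6-month follow-up". The only sensitivity analyses named in Sections 9.3 and 9.4.2 concern missing data. No analysis by source, restricted to records, or allowing for misclassification is described. The utilization index score, the EBT count and the counseling-plus-medication outcome (Sections 9.4.1 to 9.4.3) draw on the same mixture.

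Section 6.3 masks dental providers and the follow-up RA. It does not address participants.

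**The concern.** The arms differ openly in content. Intervention participants see a cessation video, receive one to two texts a day for four weeks promoting EBTs, and then get reminders until shortly before the 6-month questionnaire (Section 6.1.1). Those who ask about an EBT are asked 48 hours later whether they contacted it. Control participants see a relaxation video and receive assessment-only texts (Section 4.1). People who have been urged for months to use EBTs may be readier to say that they did.

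If that happens more in one arm, the merged endpoint carries the reporting difference into the odds ratio. Covariate adjustment does not remove it, and the missing-data analyses do not look for it. The sponsor could then claim an effect on EBT use that is partly or wholly an effect on reporting. Sections 2.1 and 2.2 themselves criticise earlier studies for lacking objective verification.

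**Working it through.** **Inputs from Section 9.2.** The power calculation is for the "primary outcome of any EBT engagement through a chi-square test at the two-sided" 0.05 level. Planning rates are 22.7% (Control) and 37.6% (Intervention). There are 455 randomised and 20% attrition, so 455 × 0.8 = 364 evaluable, or 182 per arm. The control rate averages two cited trials: (14.7 + 30.6)/2 = 22.65%. The lower figure comes from a trial reporting "29.8% in the intervention group vs. 14.7% in controls". The text gives other totals elsewhere (437 in Section 1.1, 376 in Section 4.1); 455 is used because the stated power rests on it.

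**Assumptions, not in the documents.** (a) No true effect, and a net over-report of e percentage points in Intervention only. (b) For the fix, 30% to 80% of true users appear in quitline or SmokefreeTXT records, equally in both arms.

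**Formula.** With n per arm, rates p1 and p2, and p̄ their mean:

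power ≈ Φ{ [ (p2 − p1) − 1.96·√(2p̄(1 − p̄)/n) ] / √[ (p1(1 − p1) + p2(1 − p2))/n ] }

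**The plan's own figure.** p̄ = 0.3015. The pooled standard error is √(0.4212/182) = 0.0481, and 1.96 times this is 0.0943. The unpooled standard error is √(0.4101/182) = 0.0475. So z = (0.149 − 0.0943)/0.0475 = 1.15 and power is 0.875, against the stated 0.87. Exact binomial enumeration gives 0.876. The plan's figure reproduces.

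**No true effect, e = 5 points.** p1 = 0.227, p2 = 0.277, p̄ = 0.252. The pooled standard error is 0.0455, and 1.96 times this is 0.0892. The unpooled standard error is 0.0454. So z = (0.05 − 0.0892)/0.0454 = −0.86, giving 0.194. Exact enumeration of the uncorrected chi-square gives 0.195 (0.1946).

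**Over-reporting from 0 to 10 points** (exact, two-sided, 22.7% true use in both arms, 182 per arm):

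| e (points) | False users among 182 (182 × e) | Share of true non-users (e/77.3) | Chance of p<0.05 |
|---|---|---|---|
| 0 | 0 | 0% | 5.0% |
| 3 | 5.5 | 3.9% | 10.2% |
| 5 | 9.1 | 6.5% | 19.5% |
| 8 | 14.6 | 10.3% | 40.8% |
| 10 | 18.2 | 12.9% | 57.1% |

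From 3 points upward nearly all rejections favor Intervention (9.8 of the 10.2 percentage points at e = 3). At e = 5 the figure is 17.5% for a control rate of 30.6% and 24.4% for 14.7%. Starting from 41 users in each arm, 17 extra Intervention positives (58 v 41, or 9.3 points) are needed to reach p<0.05. The planned effect is 14.9 points.

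**Power of a record-only analysis.** Both planning rates are multiplied by the share of users found in records, which keeps the planned relative effect. The calculation uses 227 per arm, that is, records for everyone randomised.

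| Share in records | Rates | Power |
|---|---|---|
| 30% | 6.8% v 11.3% | 0.38 |
| 50% | 11.4% v 18.8% | 0.60 |
| 80% | 18.2% v 30.1% | 0.85 |

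At 182 per arm the corresponding powers are 0.32, 0.51 and 0.76.

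**The case against.** The self-report is disclosed in the very section that defines the outcome. Questionnaires go out as electronic links (Section 5.5), the follow-up RA is masked and the unmasked clinic RAs collect no outcome data (Section 6.3), so interviewer pressure is limited. Controls receive the same brochure and questionnaires and may over-report too; only the net difference matters. Section 9.4.1 promises a formal SAP before unblinding, which could still add the analysis. The schedule in Section 1.3 has both self-reported EBT contact and objective confirmation, so material for a check may already be collected.

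A record-only endpoint is also a different outcome. Intervention texts carry quitline contact details and a direct SmokefreeTXT opt-in link (Section 1.1). They could move people towards the recorded channels without raising total use. Quitline confirmation depends on matching identifiers (Section 2.3.3), and matching to SmokefreeTXT is not described. Sections 2.3.3, 7.1 and 7.2 end participation for, or allow replacement of, some randomised people, so it is unclear whether records would be sought for them.

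Most of this stands. It limits what a record-only analysis can show, and it makes the size of any bias a matter of assumption. It does not supply an analysis that separates the sources, and it does not reconcile Section 2.1 with Section 9.4.2. The pending SAP makes the change easy to adopt; it does not make it unnecessary.

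**Conclusion.** The point holds. The primary endpoint is partly self-reported, Section 2.1 says otherwise without qualification, and nothing planned would show whether an observed effect rests on records or on reports. Under the stated assumptions, 3 to 5 points of net over-reporting would raise the false-positive rate from 5% to about 10% to 19%. A false positive becomes more likely than not only near 10 points.

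A reader might infer more than the documents support:

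- **That a positive result would be false.** No over-reporting rate is given, and the net bias could favor Control.
- **That participants are documented as unmasked.** They are not. Their awareness of what their arm received is a strong inference from its content. Whether they know which arm is experimental is not stated.
- **That a record-only analysis would be unbiased and could become the primary one.** It does not depend on self-report or on survey return, but it remains open to linkage misses and channel shift, and it would be underpowered under most of the shares assumed. A null result could not by itself tell over-reporting from low power.

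**What to change.** 1. Add to Section 9.4.2, and carry into the pending SAP, a supportive analysis of any record-confirmed EBT: quitline contact or NRT shipped by the quitline, or SmokefreeTXT enrolment. Use the same logistic model. Request records for all randomised participants, whether or not they return the 6-month survey. Report the odds ratio and 95% confidence interval beside the primary result, and interpret Hypothesis 1.1 in light of both.
2. If the questionnaires also ask about quitline and SmokefreeTXT use, tabulate self-report against records by arm. This estimates differential over-reporting directly for those two EBTs.
3. State the limits with the result: lower event rate and power, possible missed matches, and possible movement of Intervention users towards the channels promoted by the texts.
4. Reword Section 2.1 to say that the primary outcome is partly objective.

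The cost is one extra model, one table where the items exist, and record requests that cover everyone randomised. Quitline and SmokefreeTXT records are already planned (Sections 2.3.3 and 9.4.2). The primary analysis and the sample size do not change.
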